10.4.1 Response categories for CLL patients

Complete Response (CR)
Complete Response (with incomplete marrow recovery) (CRI)
Partial Remission (PR)
Stable Disease (SD)
Progressive Disease (PD)

10.4.2 Response categories for lymphoma patients (except those with Waldenström's macroglobulinaemia)

Complete Remission (CR)
Partial Remission (PR)
Stable Disease (SD)
Progressive Disease (PD)

10.4.3 Response categories for Waldenström's macroglobulinaemia patients

Complete Response (CR)
Very Good Partial Response (VGPR)
Partial Response (PR)
Minor Response (MR)
Stable Disease (SD)
Progressive Disease (PD)

10.4.4 Recording of response in the eCRF

The applicable overall response category for each visit that includes disease assessment must be recorded in the eCRF.

11 PATIENT WITHDRAWAL BEFORE COMPLETION OF TREATMENT SCHEDULE

The Investigator must make every reasonable effort to keep each patient on trial for the whole duration of the trial (i.e. until 4 weeks post the last BI-1206 administration in the induction phase). However, if the Investigator removes a patient from the trial or if the patient declines further participation, final 'off-study' assessments should be performed ideally before any subsequent therapeutic intervention. All the results of the evaluations and observations, together with a description of the reasons for withdrawal from the trial, must be recorded in the medical records and in the electronic case report form (eCRF).

Patients who are removed from the trial due to adverse events (clinical or laboratory) will be treated and followed according to accepted medical practice. All pertinent information concerning the outcome of such treatment must be recorded in the eCRF and on the serious adverse event (SAE) report form where necessary.

The following are justifiable reasons for the Investigator to withdraw a patient from study treatment. Every effort will be made to complete safety follow-up activities unless consent to safety follow-up has been withdrawn by the patient.

- Adverse event/serious adverse event (AE/SAE);
- Withdrawal of consent;
- Serious deviation from the trial protocol (including persistent patient attendance failure and persistent non-compliance);
- Sponsor's decision to terminate the trial;
- Withdrawal by the Investigator for clinical reasons not related to BI-1206 or rituximab.
- Evidence of disease progression;
- Pregnancy (for female patients during the study).

12 DEFINING THE END OF TRIAL

The 'end of trial' is defined as the date when:

The last patient has received their last maintenance treatment, completed their off study visit, and follow up period for related AEs (if applicable) and 1 year survival follow up has been completed for all patients.

It is the responsibility of the CDD to inform the Medicines and Healthcare products Regulatory Agency (MHRA) and the Research Ethics Committee (REC) within 90 days of the 'end of the trial' that the trial has closed.

In cases of early termination of the trial (for example, due to toxicity) or a temporary halt by the CDD, the CDD will notify the MHRA and the REC within 15 days of the decision and a detailed, written explanation for the termination/halt will be given.

Recruitment will cease when:

- The study drug (s) is/are considered too toxic to continue treatment before the required number of patients have been recruited.
- The stated number of patients to be recruited has been reached.
- The stated objectives of the trial are achieved.

Regardless of the reason for termination, all data available for patients at the time of discontinuation of follow-up must be recorded in the eCRF. All reasons for discontinuation of treatment must be documented.

In terminating the trial, CDD and the Investigators must ensure that adequate consideration is given to the protection of the patient's interest.

13 DATA ANALYSIS AND STATISTICAL CONSIDERATIONS

The final analysis will be conducted after one of the following conditions is met:

- The trial is terminated early
- The end of trial as defined in Section 12 has been reached.

13.1 Presentation of data

Data will be presented in a descriptive fashion. Variables will be analysed to determine whether the criteria for the trial conduct are met. This will include a description of patients who did not meet all the eligibility criteria, an assessment of protocol deviations, IMP accountability and other data that impact on the general conduct of the trial.

Baseline characteristics will be summarised for all enrolled patients. Patients who died or withdrew before treatment started or did not complete the required safety observations will be described and evaluated separately.

Treatment administration will be described for all cycles. Dose administration, dose modifications or delays and the duration of therapy will be described.

13.2 Safety

Safety data will be collected from the date of written consent. Safety variables will be summarised by descriptive statistics. Laboratory variables will be described using the National Cancer Institute (NCI) Common Terminology Criteria for Adverse Events (CTCAE) Version 4.02.

Adverse events (AEs) will be reported for each dose level and presented as tables of frequency of AEs by body system and by worst severity grade observed. Tables should indicate related and unrelated events.

13.3 Pharmacokinetics

The serum concentration/time data will be analysed using non-compartmental methods. The pharmacokinetic (PK) parameters to be determined for BI-1206 include the maximum observed serum concentration (C_{max}), time to reach C_{max} (T_{max}), and the area under the serum concentration time curve (AUC), and the terminal elimination half-life ($T_{1/2}$), total body clearance (CLT) and steady/state volume of distribution (V_{ss}).

13.4 Pharmacodynamics

The pharmacodynamic analyses to be performed are described below. Reports will undergo a quality control (QC) step prior to finalisation and will be signed by the person responsible for performing the assays and the laboratory Quality Assurance (QA) manager once final.

Anti-drug antibody (ADA)

The presence of anti-BI-1206-antibody responses will be assessed using ELISA and reported per patient.

B-lymphocyte levels: CD19, CD20 and CD32b

CD19 B-lymphocyte levels will be assessed and reported at each site as part of the regular haematology assessment to determine the level of peripheral blood B-lymphocyte depletion. Results will be entered onto the clinical database and provided to the analysing pharmacodynamic laboratory for comment.

CD32b and CD20/CD19 B-lymphocyte expression levels in blood will be measured using flow cytometry. Results will be reported and analysed longitudinally for each patient.

Levels of B lymphocytes will be measured in bone marrow aspirate to determine the level of bone marrow B lymphocyte depletion. Cell surface markers will be assessed using flow cytometry and results analysed longitudinally for each patient.

A horizontal bar chart with 10 categories on the y-axis and a scale from 0 to 1000 on the x-axis. The bars are black and show the following approximate values: Category 1: 100, Category 2: 900, Category 3: 100, Category 4: 900, Category 5: 100, Category 6: 100, Category 7: 100, Category 8: 100, Category 9: 100, Category 10: 100.

13.5 Anti-tumour activity

Documenting anti-tumour activity is a secondary objective of this trial. Patients must receive at least one dose of BI-1206 and/or rituximab on as part of this trial; have a baseline disease assessment and at least one follow-up disease assessment to be evaluable for response. Patients who experience clear clinical disease progression without formal post-treatment disease assessment will be included and will be considered to have progressive disease. Objective responses, the best tumour response achieved by each patient while on trial and the time to progression will be presented in the data listings.

13.6 Overall Survival and Progression-Free Survival

13.6.1 Overall Survival

All patients who receive BI-1206 and/or rituximab on as part of this trial will be evaluable for overall survival, regardless of whether they subsequently receive other anti-cancer treatments. Overall survival will be measured from the date of administration of the first dose of BI-1206 on this trial. Subgroup analyses of per protocol patients may be performed. Median overall survival will be reported. Patients who are lost to follow-up will be censored at the time of last contact, patients who start a new treatment will not be censored.

13.6.2 Progression-Free Survival

All patients who receive BI-1206 and/or rituximab as part of this study and who complete a baseline and at least one post-treatment disease assessment (or experience clear disease progression without a formal post-treatment disease assessment) will be evaluable for progression-free survival (PFS), regardless of whether they subsequently receive other anti-cancer treatments. PFS will be measured from the date of administration of the first dose of BI-1206. Subgroup analyses of per protocol patients may be performed. Median progression free survival will be reported. Patients who are lost to follow-up will be censored at the time of last recorded disease assessment, patients who start a new treatment will not be censored.

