3.1.2 Secondary objectives and endpoints

Secondary objectives	Endpoints
Parts A and B	
To determine the PK profile of BI-1206 (\pm an anti-CD20 mAb) as a single agent in patients with relapsed or refractory B cell malignancies.	Measurement of PK parameter values for BI-1206 (as a single agent and when given in combination with an anti-CD20 monoclonal antibody) during the BI-1206 treatment period including AUC, C_{max} , T_{max} , and half-life ($T_{1/2}$) in serum samples using enzyme-linked immunosorbent assay (ELISA).
To assess the immunogenicity of BI-1206 (\pm an anti-CD20 mAb) in patients with relapsed or refractory B cell malignancies.	Measurement of anti-drug antibody (ADA) response to BI-1206 (as a single agent and when given in combination with an anti-CD20 mAb) during the BI-1206 treatment period using ELISA.
To evaluate the effect of BI-1206 (\pm an anti-CD20 mAb) on the depletion of peripheral blood B cells (B lymphocytes).	Measurement of peripheral blood B-lymphocyte depletion during the BI-1206 treatment period (as a single agent and when given in combination with an anti-CD20 mAb) using flow cytometry.
To document possible anti-tumour activity of BI-1206 (\pm an anti-CD20 mAb) in patients	Assessment of best disease response according to the revised response criteria for malignant lymphoma (Cheson, 2014) Waldenström macroglobulinaemia assessment criteria (Owen 2013, Kimby 2006) or NCI chronic lymphocytic leukaemia (CLL) criteria (Hallek, 2008).
To measure the duration of response to BI-1206 (\pm an anti-CD20 monoclonal antibody) over a follow-up period of 1 year.	Measure progression free survival (PFS) and overall survival (OS) at 1 year after the first BI-1206 administration on the study for all patients.

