3.5.5 Survival

All patients receiving at least one administration of mAb (BI-1206 with/without rituximab) as part of this trial will be evaluable for survival (OS and PFS) regardless of whether they subsequently receive other anti-cancer treatments. Please see Section 7.5.2.

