5.6. Time to progression, progression-free survival, and overall survival

Time to progression (TTP) is defined as the time from study entry until objective disease progression (see Section 5.3). Progression free survival (PFS) is defined as the time from study entry until objective disease progression or death. Overall survival is defined as the time from study entry until death from any cause, and is measured in the intent-to-treat population.

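### Section 13.6.2 drops treated patients who die unassessed without clear progression from PFS, against Section 3.5.5 and the all-patients endpoint, and Section 13.6 plans medians but no 1-year estimates

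*Combined protocol and SAP*

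**What the plan says.** Three current sections describe who enters the PFS analysis.

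- **Section 3.1.2** states the secondary endpoint: "Measure progression free survival (PFS) and overall survival (OS) at 1 year after the first BI-1206 administration on the study for all patients".
- **Section 3.5.5** says that patients given at least one antibody administration "as part of this trial will be evaluable for survival (OS and PFS) regardless of whether they subsequently receive other anti-cancer treatments". No disease assessment is required.
- **Section 13.6.2** admits only treated patients "who complete a baseline and at least one post-treatment disease assessment (or experience clear disease progression without a formal post-treatment disease assessment". Time runs from the first BI-1206 dose.

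Section 13.6.1 places no assessment requirement on OS.

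Section 13.6.2 does not define the PFS event. The only definition is in the CLL criteria reproduced in Appendix 4 (5.6): "Progression free survival (PFS) is defined as the time from study entry until objective disease progression or death". On censoring, 13.6.2 says "Patients who are lost to follow-up will be censored at the time of last recorded disease assessment". For the summary statistic, 13.6.1 says "Median overall survival will be reported" and 13.6.2 says "Median progression free survival will be reported". Section 13.6 mentions no 1-year estimate.

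**The concern.** The two evaluability rules give different PFS sets from the same data, so the reported result depends on which section the analyst follows. The 13.6.2 rule closely resembles the response-evaluability rule in Section 13.5. It suits a response rate, but not a time-to-event endpoint counted from first dose, because entry to the analysis then depends on what happens after time zero.

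The patients lost are those treated who die before any post-treatment assessment and without clear progression. Their PFS times are among the shortest in the trial. They stay in the safety set (3.5.2) and the OS set (13.6.1), so the distortion is confined to PFS. In addition, the 1-year PFS and OS that the secondary endpoint asks for are not in the planned analysis.

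**Working it through.** The plan gives no PFS or OS estimate, event count or power, so there is no figure to reproduce. The check has four steps.

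**1. Who is left out.** The schedule in Section 7.6 puts the first post-baseline disease assessment at Week 8, Day 50 (+1 week).

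| Treated patient | 3.5.5 | 13.6.2 |
|---|---|---|
| Baseline and post-treatment assessment | in | in |
| Clear progression, no formal assessment | in | in |
| Dies unassessed, no clear progression | in | **out** |
| Leaves alive, unassessed, no event | in | out |

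The last row does not bias the estimate by itself. Most leavers are re-evaluated at discontinuation (7.4, 10.3.1, 10.3.3), and a patient censored at first dose adds nothing to a Kaplan-Meier curve. The third row causes the bias.

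**2. Effect on 1-year PFS.** Take a Part B arm of 25 (Section 3.2), with *k* omitted early deaths and 1-year PFS *E* in the remaining 25 − *k*. Both *k* and *E* are assumed. The omitted patients have 1-year PFS of zero, so:

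- all-treated PFS = *E* × (25 − *k*)/25
- overstatement = *E* × *k*/25

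| *E* | *k* = 1 | *k* = 2 | *k* = 3 |
|---|---|---|---|
| 30% | 1.2 points | 2.4 | 3.6 |
| 50% | 2.0 | 4.0 | 6.0 |
| 70% | 2.8 | 5.6 | 8.4 |

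At *E* = 50% the all-treated values are 48%, 46% and 44%. Simulated Kaplan-Meier estimates (4,000 arms for each *k*, *E* = 50%) gave the same 2.0, 4.0 and 6.0 points with the deaths added as early events. They gave 0.0 points with *k* patients censored at first dose instead. For scale, the 95% half-width at 50% with n = 25 is 1.96 × √(0.25/25) = 19.6 points.

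**3. Effect on the median.** Assume an exponential all-treated curve with median *m* and an omitted share *d*, all with early events. The reported curve is then the all-treated curve divided by (1 − *d*), and the reported median is *m* × log₂(2/(1 − *d*)). For 1, 2 or 3 of 25 (*d* = 4%, 8%, 12%) the median rises by 5.9%, 12.0% or 18.4%. An assumed 6.0-month median would be reported as 6.35, 6.72 or 7.11 months.

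**4. How many such deaths.** The documents do not say. An upper guide uses the background median survivals in Section 2.1.1 (about 12 months in CLL, 13 in lymphoma) and an assumed constant hazard. The share dying by Day 50 is 1 − 0.5^((50/30.4375)/median): 9.1% at 12 months and 8.4% at 13 months, or 2.3 and 2.1 of 25 patients. This counts all deaths, whereas deaths with clear progression stay in the 13.6.2 set, so the affected number is smaller.

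**The case against.** **The bias needs death to be a PFS event, and 13.6.2 does not say that it is.** This is correct as a condition. But the endpoint's name implies it, Appendix 4 states it for CLL, and Section 13.5 lists time to progression as a separate quantity. If death did not count, 13.6.2 would be reporting time to progression under another name.

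**The affected group is narrow.** Clear progression is a route in, inclusion criterion 4 requires a life expectancy of at least 12 weeks, and leavers are re-evaluated. All of this stands, and it is why the expected size is small.

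**The censoring date is a problem only if the sets are mixed.** Under 13.6.2 alone, living unassessed patients are outside the set. Under 3.5.5, their last recorded assessment is the baseline one, normally before time zero, so the 13.6.2 censoring rule gives no usable date. Adopting the 3.5.5 set therefore requires a new rule.

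**The 1-year wording may describe only a follow-up horizon.** The paired objective does speak of a one-year follow-up period, and 13.6 does not rule out other summaries. The plain reading of the endpoint is still an estimate at 1 year, and no section plans one.

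**PFS is secondary and descriptive, and no dose decision uses it.** True. This limits the consequence but does not settle which set to analyse.

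**Conclusion.** The concern holds. Section 13.6.2 contradicts Sections 3.5.5 and 3.1.2 on the PFS population, and the 1-year estimates named in the endpoint are not planned. The textual conflict depends on no assumption. The upward direction rests on death counting as a PFS event and on at least one such death occurring. The size cannot be fixed from the documents: across the assumed range (1 to 3 of 25 patients, 1-year PFS of 30% to 70%) it is 1.2 to 8.4 points, below the sampling error of one arm but always favourable. The primary endpoint, the dose decisions and OS are not biased by it. It should be corrected before the final analysis, so that the set is not chosen after the data are seen.

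**What to change.** In Section 13.6.2:

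1. Use the Section 3.5.5 set, all treated patients.
2. Define the event, for all histologies, as progression or death from any cause, timed from the first BI-1206 dose. Say explicitly how a later death is handled in a patient who left without a post-baseline assessment.
3. Censor event-free patients with no post-baseline assessment at first dose.

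In Sections 13.6.1 and 13.6.2:

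4. Report Kaplan-Meier 1-year OS and PFS with 95% confidence intervals by arm, beside the medians, and state whether Part A patients are pooled with Part B.

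The cost is a short wording change and a few extra tables from data already collected. Reported PFS may look slightly less favourable.

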14 ADMINISTRATION

This trial is conducted under a clinical trial authorisation (CTA) and approval from the Medicines and Healthcare products Regulatory Agency (MHRA) and the relevant Research Ethics Committee(s) (REC) will be obtained before the start of this trial. This trial is sponsored and monitored by Cancer Research UK's Centre for Drug Development (CDD). Applicable regulatory requirements are described in this section.

14.1 Protocol deviations and amendments

The protocol should be adhered to throughout the conduct of the study, if a situation arises where the conduct of the study may not be in line with the protocol, then site should contact the CDD to discuss this.

Amendments to the protocol may only be made with the approval of the CDD. A protocol amendment may be subject to review by the assigned Ethics Committee, Health Research Authority (HRA) and the MHRA. Written documentation of the Ethics Committee and HRA (and if appropriate the MHRA) 'favourable opinion' (i.e. approval) must be received before the amendment can be implemented and incorporated into the protocol if necessary.

14.2 Serious breach of Good Clinical Practice

A serious breach is a breach which is likely to effect to a significant degree: the safety or physical or mental integrity of the subjects of the trial, or the scientific value of the trial.

In order that the Sponsor can fulfil their obligations in terms of reporting serious breaches of Good Clinical Practice (GCP) to the MHRA within seven calendar days of identification, site staff must inform the Sponsor of any unplanned deviations to the trial protocol (or GCP principles) as soon as possible after the deviation occurs to allow prompt evaluation by the Sponsor.

14.3 Completion of the electronic case report form

Electronic case report forms (eCRFs) approved and maintained by the CDD will be used to collect the data. The Investigator is responsible for ensuring the accuracy, completeness, clarity and timeliness of the data reported in the eCRFs.

Only the Investigator and those personnel who have signed the Delegation Log provided by the CDD and have been authorised by the Investigator should enter or change data in the eCRFs. Authorised users will be included on a user list in order to be provided access to the eCRF. All protocol required investigations must be reported in the eCRF. The Investigators must retain all original reports, traces and images from these investigations for future reference.

The collection and processing of personal data from the patients enrolled in this clinical trial will be limited to those data that are necessary to investigate the efficacy, safety, quality and usefulness of the study drug used in this trial. The data must be collected and processed with adequate precautions to ensure patient confidentiality and compliance with applicable data privacy protection according to the applicable regulations. The data collected will comply with Directive 95/46/EC of the European Parliament and of the Council of 24 October 1995 on the protection of individuals with regard to the processing of personal data.

Data will be entered directly into electronic screens by authorised site personnel. Amendments to eCRF data will be made directly to the system and the system audit trail will retain details of the original value(s), who made the change, a date and time, and a reason for the change.

Once an eCRF form has been entered by the site personnel, the data are cleaned using manual and automated checks. Queries will be issued electronically to the site. Authorised personnel must answer the queries by making relevant amendments to data or providing a response. Answered queries will be closed or reissued as appropriate.

Once the patient is 'off study' and the eCRF has been fully completed, the Investigator must provide an electronic signature to authorise the complete subject casebook.

At the end of the trial all eCRFs are retained and archived by the CDD and a PDF copy provided to the Investigator who is responsible for archiving at site.

14.4 Trial performance, monitoring, auditing and inspection

Before the trial can be initiated, the prerequisites for conducting the trial must be clarified and the organisational preparations made with the trial centre. The CDD must be informed immediately of any change in the personnel involved in the conduct of the trial.

During the trial the CDD Clinical Research Associate (CRA) will be responsible for monitoring data quality in accordance with CDD's standard operating procedures (SOPs). A strategic monitoring approach, including targeted source data verification, will be implemented where appropriate.

Before the study start, the Investigator will be advised of the anticipated frequency of the monitoring visits. The Investigator will receive reasonable notification before each monitoring visit.

It is the responsibility of the CRA to:

- review trial records and compare them with source documents;
- check pharmacokinetic and pharmacodynamic samples and storage;
- discuss the conduct of the trial and the emerging problems with the Investigator;
- check that the drug storage, dispensing and retrieval are reliable and appropriate; and
- verify that the available facilities remain acceptable.

At the end of the trial all unused BI-1206 supplied must be destroyed at site (only once authorised to do so by the CRA or CSM) or if authorised by Cancer Research UK returned to the supplier.

It is the responsibility of the Sponsor to notify the REC of the 'end of the trial'. (see definition in Section 12).

During the course of the trial, the Quality Assurance Department of the CDD, or external auditors contracted by the CDD, may conduct an on-site audit visit (ICH Topic E6 (R2) Guideline for Good Clinical Practice Sections 1.6).

Principal Investigators conducting this trial will accept the potential for inspection by the MHRA.

